1.2. Study Design

Overview of Study Design and Key Features	
 
Total N=1020
 
Randomize 1:1:1
 
 Sotrovimab 500mg IV (N=340) Sotrovimab 500mg IM (N=340) Sotrovimab 250mg IM (N=340) 	 
36 Week Follow Up
 
Interim analysis (~50% of participants)

Design Features
 
 • This study is a Phase 3 randomized, multi-center, open label, non-inferiority study of intramuscular (IM) versus intravenous (IV) administration of sotrovimab, a monoclonal antibody (mAb) against SARS-CoV-2 for the treatment of mild/moderate COVID-19 in participants aged 12 years and older at high risk of disease progression. • Approximately 1020 participants will be enrolled and randomized 1:1:1 to receive a single 500 mg IV infusion of sotrovimab, a single 500 mg IM injection of sotrovimab, or a single 250 mg IM injection of sotrovimab. • Participants with early, mild/moderate COVID-19 who are not on supplementary oxygen and are at risk for disease progression will receive an IV infusion or IM injection of sotrovimab. The intravenous sotrovimab dose will be 500 mg and will be infused over 15 minutes. The intramuscular sotrovimab dose will be either 250 mg or 500 mg given at a single timepoint. The 250 mg IM dose will be given either as a single 250 mg (4ml) injection in the dorsogluteal muscle or as two 2ml injections in each deltoid muscle. The 500 mg IM dose will be administered as two 4ml injections in each dorsogluteal muscle. • After IV infusion or IM injection, participants will be monitored for 30 minutes with vital signs assessments performed every 15 minutes. Injection site reaction assessments, for IM arms only, will be performed at 15 and 30 minutes after injection. 	

Overview of Study Design and Key Features	
	
 • All participants will be actively monitored on an outpatient basis with frequent collection of nasopharyngeal swabs for virology and blood draws for PK sampling and safety labs, as well as in-clinic evaluations at Weeks 1, 2, 3, 4, 12, 20 and 24 as detailed in the Schedule of Activities. • Starting at Week 8, participants will be monitored monthly via phone call or in-clinic evaluation to assess for the incidence and severity of subsequent COVID-19 illness, if any, for a total of 36 weeks from dosing.
Study intervention	
 • VIR-7831 500mg IV or VIR-7831 500mg IM or VIR-7831 250mg IM • All participants will receive SoC as per institutional protocols, in addition to the study intervention.
Study intervention Assignment	
 • Participants with early, mild/moderate COVID-19 who are not on supplementary oxygen and at risk for disease progression will be randomised 1:1:1 to receive a single dose of VIR-7831 500mg IV, VIR-7831 500mg IM or VIR-7831 250mg IM. 
Participants will be stratified based on:
 
 1. Age: 12-17 years old, 18-64 years old, and ≥ 65 years old 2. COVID-19 Vaccination History: receipt of any COVID-19 vaccine (yes, no) 3. Region of the world (North America, South America, Europe, South Asia, Rest of Asia, Rest of the World). 
 • All participants will be centrally randomized using an Interactive Web Response System (IWRS). • Participants will receive sotrovimab either by IM or IV directly from the investigator or designee, under medical supervision. The date and start and stop times of the dose administered will be recorded in the source documents. The dose of study intervention and study participant identification will be confirmed at the time of dosing by a member of the study site staff other than the person administering the study intervention.
Interim Analysis	
 • The Joint Safety Review Team (JSRT) comprising individuals from Vir and GSK will review safety data at regular intervals throughout the conduct of the study. Details of the JSRT process is recorded in relevant SRT documents. • If, during its regular scheduled review of study data, the JSRT identifies a potential safety signal, Vir may request an ad hoc meeting of the IDMC to review data for further evaluation. • An interim analysis was planned (see Protocol Amendment Version 2) once 50% of the planned number of participants had completed the Day 29 assessment. However, prior to the time of the planned analysis, the JSRT noted a discrepancy in the rate of progression to hospitalization occurring in

Overview of Study Design and Key Features	
	
the 250mg IM arm compared with the 500mg IM and IV arms. Upon review of the cumulative data, the JSRT made the decision to pause enrollment into the 250mg IM arm on 04-August-2021 and escalated the issue to the IDMC.
 
 • An ad hoc meeting of the IDMC was called on 11-August-2021 and based upon their review of the data, the IDMC concurred that enrollment in the 250mg IM arm should be discontinued. As this ad hoc IDMC meeting occurred prior to the timepoint when the formal interim analysis would have occurred and concluded with discontinuing one arm of the study combined with an unexpected rapid increase in the rate of enrollment, it was not feasible to conduct the formal interim analysis. • Therefore, data for the 250mg IM arm will be summarised only and not used for any statistical hypotheses tests or analyses.

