### 2.3. Benefit/Risk Assessment

## 2.3.1. Risk Assessment

Potential Risk of Clinical Significance	Summary of Data/Rationale for Risk	Mitigation Strategy
Study Intervention: Sotrovimab		
Infusion reactions including hypersensitivity reactions (HSR)	
While sotrovimab is a fully human IgG, Systemic reactions (SR), including hypersensitivity reactions, are a potential general risk associated with the mAb class of therapeutics.
 
Given the totality of pre-clinical and clinical data to date it is the Sponsor's position that a up to 3000 mg dose may be safely used in individuals with mild to moderate COVID-19.
 
There was no evidence of systemic infusion reactions in toxicology studies were conducted with sotrovimab in monkeys.
 
Available safety data from the clinical development program comes from evaluation of a 500 mg dose of sotrovimab administered by IV infusion, a 500 mg and a 250 mg dose administered by IM injection for early treatment of COVID-19, and a 1000 mg dose currently being evaluated in an ongoing clinical study in hospitalized participants with severe COVID-19. Safety data from the clinical program to date have demonstrated a low rate of adverse events at the time of Day 29 analysis, particularly SAE and Grade 3-4 AEs. The COMET-ICE (Phase 2/3) and COMET-TAIL (Phase 3) studies demonstrated infrequent Grade 3 and 4 AEs and SAEs in the treatment groups.
 
COMET-TAIL did not demonstrate a pattern of incrementing safety findings associated with increasing dose or exposure as it compared 250 mg IM to 500 mg IM and 500 mg IV dosing.
	
Participant selection: Participants will be excluded if they have a history of hypersensitivity to any of the excipients present in the investigational product.
 
Monitoring:
 
 
During the Lead-In phase, participants will be monitored regularly at 15 minutes, 30 minutes, 45 minutes, 1 hour, and 2 hours post-administration of study treatment (including vital signs, see the SoA in Section 1.3). Post-infusion monitoring time will only be reduced to 1 hour for additional participants enrolled after the lead in phase is complete.
 
A Joint Safety Review Team (JSRT) review will be conducted at regular intervals, inclusive of active monitoring of lead-in data. 
 
JSRT will review safety data before completing full cohort enrollment (after lead in phases), before any dose escalation (to review safety of the dose just prior to it) and before any decreases in infusion times (to review safety of the infusion time just prior to it)
 
 
 

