#### **8.4.3. Method of Detecting AEs and SAEs**

Care will be taken not to introduce bias when detecting AEs and/or SAEs. Open-ended and non-leading verbal questioning of the participant is the preferred method to inquire about AE occurrence.

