4.5.2. Adverse Events

Adverse events analyses including the analysis of adverse events (AEs), Serious AEs (SAEs) and other significant AEs will be based on GSK Core Data Standards. As per the protocol, AEs are collected through Week 12 and SAEs collected through Week 36.

An overview summary of AEs will be produced, including counts and percentages of participants with:

- AEs
- AEs related to study intervention
- AEs leading to permanent discontinuation of study intervention,
- AEs leading to temporary interruption of study intervention
- Grade 3 and 4 AEs
- Grade 3 and 4 AEs related to study intervention,
- Grade 3 and 4 AEs leading to permanent discontinuation of study intervention,
- Grade 3 and 4 AEs leading to temporary interruption of study intervention
- SAEs
- SAEs related to study intervention,
- Fatal SAEs
- Fatal SAEs related to study intervention.
- Local infusion/injection site reactions

Adverse events will be coded using the latest version of the standard Medical Dictionary for Regulatory Affairs (MedDRA dictionary) and graded by the investigator according to the DAIDS 2017 v2.1.

The following adverse events will be considered of special interest (AESI) and will be summarised using frequency and percentages separately.

- Systemic infusion/injection related reactions (IRR) including hypersensitivity reactions (HSR); reactions within 24 hours of start of infusion will be identified using a list of MedDRA preferred terms confirmed by the Safety team.
- Local infusion/injection site reactions (ISR) will be identified using a list of MedDRA preferred terms confirmed by the Safety team.
- Immunogenicity (Anti-Drug Antibodies (ADA)) related adverse drug reactions will be reported. These potential events of ADAs will be detected by reviewing AEs that indicate HSR in those subjects who have positive anti-drug antibodies.
- Adverse events potentially related to antibody-dependent enhancement of disease (ADE) will be reported. These potential events of ADEs will be detected by reviewing adverse event/serious adverse events for an increase in the incidence and severity of COVID complications for a participant that cannot be explained by underlying risk factors.

In addition to the AE overview summary,

- Most common AEs defined as any AE preferred term (PT) with an incidence of at least $\geq 1\%$ (approx. 2 subjects) in any of the treatment group will be summarised using frequency and percentages separately.

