- AEs by severity will be presented. The summary will use the following algorithms for counting the participant:
 - Preferred term row: Participants experiencing the same AE preferred term several times with different grades will only be counted once with the maximum grade.
 - Any event row: Each participant with at least one adverse event will be counted only once at the maximum grade no matter how many events they have.

The frequency and percentage of AEs (all grades) will be summarized and displayed in descending order by system organ class (SOC) and PT.

In the SOC row, the number of participants with multiple events under the same SOC will be counted once.

A separate summary will be provided for study intervention-related AEs. A study intervention-related AE is defined as an AE for which the investigator classifies the possible relationship to study intervention as “Yes”.

A worst-case scenario approach will be taken to handle missing relatedness data, i.e. the summary table will include events with the relationship to study intervention as ‘Yes’ or missing. The summary table will be displayed by PT only.

All SAEs will be tabulated based on the number and percentage of participants who experienced the event. Separate listings will also be provided for study intervention-related SAEs.

A study intervention-related SAE is defined as an SAE for which the investigator classifies the relationship to study intervention as “Yes”. A worst-case scenario approach will be taken to handle missing data, i.e. the summary table will include events with the relationship to study intervention as ‘Yes’ or missing.

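### Scheduled site checks in the IM arms only leave the any-AE, related-AE and any-AESI rows with unequal ascertainment of local reactions between IM and IV

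*SAP*

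**What the plan says.** **Observation after dosing (SAP 1.2).** General monitoring does not differ by arm: "After IV infusion or IM injection, participants will be monitored for 30 minutes with vital signs assessments performed every 15 minutes". The site check does: "Injection site reaction assessments, for IM arms only, will be performed at 15 and 30 minutes after injection". No corresponding scheduled check of the infusion site is described for the IV arm.

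**How local reactions are counted (SAP 4.5.2).** The overview table is introduced with "An overview summary of AEs will be produced, including counts and percentages of participants with". Its rows include all AEs, AEs related to study intervention, and a row of its own for local infusion or injection site reactions. Local reactions also appear in the AESI list, for both routes: "Local infusion/injection site reactions (ISR) will be identified using a list of MedDRA preferred terms confirmed by the Safety team". On display, the SAP says: "The following adverse events will be considered of special interest (AESI) and will be summarised using frequency and percentages separately". On relatedness it adds: "A separate summary will be provided for study intervention-related AEs". An event with missing relatedness is counted as related.

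**Composite AESI row (SAP 4.3.1.1).** The secondary safety overview has a row for participants with any AESI.

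**Where the comparison is used.** Describing the safety of IM and IV sotrovimab is a secondary objective (SAP 1.1). Protocol 2.3.1 later says, of 250 mg IM, 500 mg IM and 500 mg IV: "COMET-TAIL did not demonstrate a pattern of incrementing safety findings associated with increasing dose or exposure".

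**The concern.** An event that staff look for at two fixed times is more likely to be recorded than one left to spontaneous report or open questioning. If local reactions are sought in the IM arms and not in the IV arm, a row that includes them can show more events on IM even when the true rates are equal. The effect runs towards higher IM rates, so it could also hide a modestly higher rate of other AEs on IV.

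At stake is the reading of the three summary rows that most readers look at first. The safety displays are counts and percentages with no test behind them, so those percentages are the comparison. No efficacy analysis is involved.

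**Working it through.** The plan gives no figure for this point. The check is a trace through the text, followed by an illustration with assumed rates.

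**Step 1. Which rows contain local reactions?** They are identified by MedDRA preferred term, so they are coded AEs.

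| Display | Local reactions included? | Affected? |
|---|---|---|
| Any AE (SAP 4.5.2) | Yes, nothing removes them | Yes |
| Any related AE (SAP 4.5.2) | Yes, if judged related or relatedness is missing | Yes |
| Any AESI (SAP 4.3.1.1) | Yes, they are a listed AESI | Yes |
| Most common AEs; tables by preferred term | Only on their own lines | Other terms are not |
| Separate local-reaction row and AESI summary | By definition | Visible there, but without a note on the IM-only checks |
| SAEs, Grade 3-4 AEs | Only if serious or severe | Unlikely to move much |

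**Step 2. Does the separate local-reaction row let a reader undo the mixing?** Not exactly. One participant can have both a local and a non-local AE. If A participants have any AE and R have a local reaction, the number with a non-local AE lies between A - R and A. With an assumed 5% local-reaction rate and the 340 planned per arm (SAP 5), R = 0.05 x 340 = 17, so the interval is 17 participants, or 5 percentage points, wide. Only a planned row closes it.

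**Step 3. How large could the effect be?** All three inputs are assumptions:
- b = non-local AE rate, equal in both arms: 5-20%
- L = true local-reaction rate, equal in both arms: 2-10%
- s = share of local reactions recorded in the IV arm relative to IM: 0.25-0.70

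Treating local and non-local events as independent:
- IM any-AE rate = 1 - (1 - b)(1 - L)
- IV any-AE rate = 1 - (1 - b)(1 - L x s)
- Difference = (1 - b) x L x (1 - s)

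| b | L | s | IM | IV | Difference | Of 340 |
|---|---|---|---|---|---|---|
| 20% | 2% | 0.70 | 21.60% | 21.12% | 0.80 x 0.02 x 0.30 = 0.48 points | 1.6 |
| 10% | 5% | 0.50 | 14.50% | 12.25% | 0.90 x 0.05 x 0.50 = 2.25 points | 7.7 |
| 5% | 10% | 0.25 | 14.50% | 7.38% | 0.95 x 0.10 x 0.75 = 7.1 points | 24.2 |
| any | any | 1.00 | equal | equal | 0 | 0 |

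The first and third rows are the extremes of the assumed ranges.

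**Step 4. What could the middle case hide?** The two any-AE rows are equal when (1 - x)(1 - 0.05 x 0.50) = 0.855, where x is the IV non-local AE rate. This gives x = 1 - 0.855/0.975 = 12.3%. A true IV non-local rate of 12.3% against 10% on IM would then show no difference in the any-AE row.

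**Step 5. The related-AE row.** If few other events are judged related and all local reactions are (both assumptions), b is near zero and the difference approaches L x (1 - s), for example 0.05 x 0.50 = 2.5 points.

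**The case against.** The case against giving this much weight is good in several respects.

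- **Ascertainment is otherwise equal.** A reader might infer that the IV arm had the least AE ascertainment overall. The documents do not support that. Post-dose monitoring, vital signs, visits, AE collection through Week 12 and SAE collection through Week 36 are common to all arms. The gap is shown for local reactions only, and the scheduled checks end at 30 minutes.
- **Much is already displayed.** Local reactions have their own overview row and AESI summary, apart from systemic reactions. This stands, and it limits the problem to three composite rows. It does not remove it, for the reason in Step 2 of the working.
- **The link to higher doses is weak.** A reader might infer that the support for 2000-3000 mg rests on a biased comparison. The Protocol 2.3.1 sentence sits in the row on infusion and hypersensitivity reactions, next to text that stresses SAEs and Grade 3-4 AEs. It does not say that it was drawn from an any-AE total. The 250 mg IM versus 500 mg IM contrast had the same site checks. The protocol also relies on nonclinical margins. Nor do the documents give an IM exposure figure, so calling 500 mg IV the highest-exposure arm is an assumption.
- **The size is assumed.** Equal true local-reaction rates for injection and infusion have no support in the documents, and a real route effect would look the same. This stands in full.
- **The record is incomplete.** The SAP is based on Amendment 3, but the protocol at hand is Amendment 4. The earlier schedule of activities, the CRF and the Output and Programming Specification are not available. Amendment 4 names "Open-ended and non-leading verbal questioning of the participant is the preferred method to inquire about AE occurrence", yet Protocol 10.3.1 also treats infusion reactions as events about which participants are specifically asked. If earlier amendments did the same, IV capture may have been better than assumed here. Whether scheduled findings were recorded apart from spontaneous reports cannot be settled.

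**Conclusion.** The point holds as a modest reporting correction. On the SAP's own words, local reactions were checked on schedule in the IM arms only, and they enter the any-AE, related-AE and any-AESI rows with no planned row that excludes them. The IM-versus-IV difference in those rows cannot be read as a pure difference in safety.

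The size cannot be derived from the documents. Under the assumed ranges it is roughly 0.5 to 7 percentage points in the any-AE row. It is zero if IV capture was as complete as IM capture. Part or all of any excess of local reactions on IM may be a true effect of the route, and the design cannot separate the two.

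The documents do not support extending this to the serious, severe or systemic-reaction displays, or to a claim that the Protocol 2.3.1 statement is wrong.

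**What to change.** In SAP 4.5.2, and in the overview in SAP 4.3.1.1:

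1. Add any-AE, related-AE and any-AESI rows that exclude local infusion/injection site reactions, using the preferred-term list the SAP already calls for. Base IM-versus-IV safety statements on these rows.
2. Footnote the existing local-reaction row to say that scheduled site assessments at 15 and 30 minutes were made in the IM arms only.

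Any IM-versus-IV part of the Protocol 2.3.1 statement on dose or exposure should be checked against the rows without local reactions.

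The cost is some SAP wording and a few table rows from events that are coded anyway; no new data are needed. The drawback is that three totals appear twice. Protocol 2.1 already quotes Day 29 results, so for that report the rows may have to be supplied as a supplementary table and labelled as added later.

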2. STATISTICAL HYPOTHESES

The primary objective of this study is to evaluate the efficacy of IM sotrovimab versus IV sotrovimab in preventing the progression of mild/moderate COVID-19 in a non-inferiority comparison.

The primary endpoint is progression of COVID-19 through Day 29 as defined by hospitalization > 24 hours for acute management of illness OR death.

Denoting the proportions of participants with progression of COVID-19 by Day 29 in the sotrovimab 500 mg IM arm, sotrovimab 250 mg IM arm and sotrovimab 500 mg IV arm as P_{IM500} , P_{IM250} and P_{IV500} , respectively, then the null (H_0) and alternative (H_A) hypotheses are as follows using a non-inferiority margin of 3.5% (per feedback from the FDA, as mentioned in protocol section 4.2) on the risk difference scale:

(1) Sotrovimab 500 mg IM vs sotrovimab 500 mg IV:

- $H_0: P_{IM500} - P_{IV500} \geq 3.5\%$. $H_A: P_{IM500} - P_{IV500} < 3.5\%$

(2) Sotrovimab 250 mg IM vs sotrovimab 500 mg IV:

- $H_0: P_{IM250} - P_{IV500} \geq 3.5\%$. $H_A: P_{IM250} - P_{IV500} < 3.5\%$

2.1. Multiplicity Adjustment

Hypotheses (1) and (2) above will be tested using the primary estimand according to the hierarchical testing principal as follows:

- If the null hypothesis for (1) is rejected, i.e., the upper bound of the two-sided 95% confidence interval for the risk difference between sotrovimab 500 mg IM and

sotrovimab 500 mg IV is less than the pre-specified 3.5% non-inferiority margin, then hypothesis for (2) will be tested.

- If the null hypothesis for (1) is not rejected, then hypothesis for (2) will not be tested.

Below is a summary of possible outcomes of the hierarchical testing procedure:

Which Null Hypothesis is Rejected	Non-inferiority Declared For
Hypotheses (1) and (2)	Both sotrovimab 500 mg IM and sotrovimab 250 mg IM (vs. sotrovimab 500 mg IV)
Hypothesis (1) but Not (2)	Only sotrovimab 500 mg IM vs. sotrovimab 500 mg IV
Hypothesis (1) is NOT rejected (Null hypothesis for (2) won't be tested in this case)	Neither sotrovimab 500mg IM nor sotrovimab 250mg IM (vs sotrovimab 500mg IV)

Two secondary endpoints will be formally analysed:

- 1) Mean area under the curve of SARS-CoV-2 viral load in nasal secretions as measured by qRT-PCR from Day 1 to Day 8 (AUC_{D1-8}). Each IM dose will be assessed for equivalence to IV based on the two-sided 90% confidence interval for the treatment ratio falling within equivalence bounds of 0.5 to 2.0.
- 2) Progression of COVID-19 through Day 29 as defined by visit to a hospital emergency room for management of illness OR Hospitalization for acute management of illness for any duration and for any cause OR Death. Each IM dose will be assessed for non-inferiority vs IV using a non-inferiority margin of 3.5% on the risk difference scale.

The testing of the two secondary endpoints above is adjusted for multiplicity by using the following hierarchy:

- Secondary endpoint (1) will only be tested if non-inferiority is achieved for sotrovimab 500 mg IM vs. sotrovimab 500 mg IV and sotrovimab 250 mg IM vs. sotrovimab 500 mg IV comparisons for the primary endpoint.
- Secondary endpoint (1) will be tested in the same sequential way as the primary endpoint i.e If the null hypothesis for sotrovimab 500 mg IM vs. sotrovimab 500 mg IV is rejected, then the null hypothesis for sotrovimab 250 mg IM vs. sotrovimab 500 mg IV will be tested. If the null hypothesis for sotrovimab 250 mg IM vs sotrovimab 500mg IV for secondary endpoint (1) is rejected, then secondary endpoint (2) will be tested in the same sequential manner as secondary endpoint (1).

Given that recruitment to the sotrovimab 250 mg IM arm was permanently discontinued following the *ad hoc* interim analysis on 11-Aug-2021, the sotrovimab 250 mg IM arm will not

be formally compared to the sotrovimab 500 mg IV arm. Therefore only hypotheses for primary and secondary endpoints related to the 500 mg IM arm will be formally tested in the above framework and hypotheses related to the 250 mg IM arm are removed from the testing hierarchy.

